7.3. Safety Variables

The primary safety endpoint is the subject incidence of adverse events.

Other safety endpoints include:

- Changes from baseline in all safety laboratory parameters;
- Changes from baseline in vital signs.

8. ANALYSIS POPULATIONS

The following subject populations will be evaluated and used for presentation and analysis of the data:

- **Safety Population** includes of all subjects who have received at least one dose of study drug.

- **Modified Intent-to-Treatment (mITT) Population** includes all subjects who have received at least one dose of study drug, and have at least one post baseline urinary PCR assessment.
- **Per-Protocol (pP) Population** includes all mITT subjects who have complied with the protocol for the study drug administration, have been on stable RAAS dose, and not taken protocol-prohibited concomitant medications.

The Safety population will be used for the summaries of disposition, demographics, baseline characteristics, medical history, and prior/concomitant medications. Additionally, the Safety population will be used for the summaries of adverse events, laboratory tests, ECG, and vital signs.

The mITT and pP populations will be used for the summaries of the efficacy endpoints.

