- Two bottles of CCX168 study medication will be dispensed to the subject, with dosing instructions;

- The subject will be asked to take the first dose of study medication, 3 x 10 mg CCX168 capsules, while at the study center; the time of dosing will be recorded;
- Blood samples will be collected at 0.5, 1, 2, 3, 4, and 6 hours following CCX168 dosing for plasma CCX168 concentration measurements; the actual time of each blood sample collection will be recorded;
- Any post-dosing adverse events will be recorded;
- After all study procedures have been completed, the subject will be reminded to:
 - Come to the study center for the Day 8 study visit with their first morning urine sample;
 - Store the study medications in a cool and dry place according to label instructions for the duration of the study;
 - Take the CCX168 medication every morning and in the evening approximately 12 hours after the morning dose;
 - Not to take CCX168 medication on the morning of Day 8, unless the visit is scheduled in the afternoon, in which case CCX168 medication should be taken the morning of Day 8;
 - To bring all study medication bottles, whether empty or not, when s/he comes back for the next study visit, and
 - Continue taking their RAAS blocker(s) at a stable dose, and all their other concomitant medications as usual.

6.5. Study Day 8

The Study Day 8 visit must occur on the scheduled date. The subject will visit the study center on Day 8 for the following procedures:

- Vital signs (temperature, blood pressure, heart rate) will be measured supine after at least 3 minutes of rest;
- Serum chemistry and hematology; an eGFR will be calculated;
- Urinalysis, including pH, specific gravity, glucose, nitrite, ketones, bilirubin, urobilinogen, RBCs, and WBCs on a first morning urine sample collection;
- Urinary protein, creatinine, albumin, MCP-1, EGF, and microscopic RBC count on a first morning urine sample collection;
- Plasma samples will be collected for PD marker and PK assessment; the time of sample collection as well as the date and time of the last dose of CCX168 prior to sample collection will be recorded;
- A urine sample will be collected for PD marker assessment;
- Any changes in concomitant medication use will be recorded;
- Study drug accountability will be performed on all returned study medication;

- Two bottles of CCX168 study medication will be dispensed to the subject, with dosing instructions;

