7.6. Subject Populations

For the purposes of data analysis, the ITT Population will include all subjects who are enrolled, have received at least one dose of study drug, and have at least one post baseline urinary PCR assessment. The safety population will include all subjects who are randomized and have received at least one dose of study drug. A per protocol (PP) population may also be defined if there are major protocol deviations that could affect study outcome.

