9.3. Data Presentation

The following rules describe reporting conventions for the study.

- Report output will be provided as Rich Text Format (RTF) or Portable Document Format (PDF) documents generated using SAS.
- Font – Courier New or SAS font with minimum of 9 point font size for tables and 7 point for listings.
- Margins – Minimum of 3/4" bound edge margin and 3/8" other margins on 8.5"x11" paper as per the FDA guidance for e-submission.
- Continuous data will be summarized using n (number of subjects with non-missing observations), mean, median, standard deviation (STD), minimum value, and maximum value. Geometric means and geometric mean ratios (Visit:Baseline) will also be provided for urinary PCR, ACR, RBC count, MCP-1:creatinine, EGF:MCP-1 ratio, EGF:MCP-1 ratio, and serum IgA:plasma C3 ratio. Confidence intervals will also be provided for efficacy parameters.

- Categorical data will be summarized using the frequency count and percentage (n, %) of subjects in each category. Confidence interval for the percentage will be calculated for the efficacy variables.
- Number of subjects with non-missing values or number of subjects with missing values (eg, Not Done) will be presented, where appropriate. Subjects with missing values will not contribute to the denominator of percentage calculations.
- Counts of zero in any category will be presented without percentage.
- Precision of summary statistics:
 - Sample size (n, N) and number of missing responses (if displayed) – Integer.
 - Mean, confidence interval – One additional decimal place than reported/collected.
 - Standard deviation – Two additional decimal places than reported/collected.
 - Median, other percentile, minimum, maximum – Same number of decimal places as reported/collected.
 - Ratios – two decimal places.
 - Percentages – one decimal place generally, or two decimal places for <0.1%.
- Data listings will include pertinent subject information, eg, treatment, age/gender/race, study day. These will be sorted in the order of subject ID, assessment date/time and assessment (in the order collected on CRF, unless specified otherwise).
- Dates will be presented in the ISO-8601 format YYYY-MM-DD. Times will be displayed in 24-hour clock format.
- Numbering for tables, figures and listings will follow ICH E3 Guidelines.

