10.7.2. Proportion of subjects achieving renal response

Renal response is defined as (1) a decrease in proteinuria from baseline to Day 85 to a level of <300 mg/g creatinine and (2) maintaining the Day 85 estimated glomerular filtration rate (eGFR) within 15% of baseline. The number (%) of subjects achieving renal response will be calculated and presented. Subjects who discontinued prior to Week 12 will be counted as non-responders.

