APPENDIX A
List of Tables, Listings, and Figures

NUMBER	TITLE	POPULATION
Tables		
14.1.1.1	Disposition	MITT
14.1.1.2	Disposition	Safety
14.1.2.1	Subject Demographics	MITT
14.1.2.2	Subject Demographics	Safety
14.1.3	Baseline IgA Nephropathy Duration	Safety
14.1.4.1	Study Drug Exposure	MITT
14.1.4.2	Study Drug Exposure	Safety
14.1.5	Prior Medications by WHODD Anatomic Therapeutic Chemical Classification and Preferred Term	Safety
14.1.6	Concomitant Medications by WHODD Anatomic Therapeutic Chemical Classification and Preferred Term	Safety
14.2.1.1	Change from Baseline in Slope of Urinary Protein to Creatinine Ratio (PCR)	MITT
14.2.1.2	Change from Baseline in Slope of Urinary Protein to Creatinine Ratio (PCR)	PP
14.2.2.1	Subjects Achieving Renal Response	MITT
14.2.2.2	Subjects Achieving Renal Response	PP
14.2.3	Change from Baseline in Slope of Urinary Albumin to Creatinine Ration (ACR)	MITT
14.2.4	Change from Baseline in Slope of Urinary Estimated Glomerular Filtration Rate (eGFR)	MITT
14.2.5	Change from Baseline in Slope of Urinary MCP-1 to Creatinine Ratio	MITT
14.2.6	Change from Baseline in Slope of Urinary Epidermal Growth Factor (EGF) to MCP-1 Ratio	MITT
14.2.7	Change from Baseline in Slope of Urinary Microscopic Red Blood Cell (RBC) Counts	MITT
14.2.8	Percent Change from Baseline in Urinary Protein to Creatinine Ratio	MITT
14.2.9	Percent Change from Baseline in Urinary Albumin Creatinine Ratio	MITT
14.2.10	Percent Change from Baseline in Urinary RBC Count	MITT
14.2.11	Change from Baseline in eGFR	MITT
14.2.12	Percent Change from Baseline in Urinary MCP-1 to Creatinine Ratio	MITT
14.2.13	Percent Change from Baseline in Serum IgA to Plasma C3 Ratio	MITT
14.2.14	Percent Change from Baseline in Urinary EGF to MCP-1 Ratio	MITT
14.2.15	Shift in Urinary PCR from Baseline to Visit	MITT
14.2.16	Shift in Urinary ACR from Baseline to Visit	MITT
14.2.17	Shift in Urinary RBC from Baseline to Visit	MITT
14.3.1.1.1	Overall Summary of Treatment-Emergent Adverse Events	Safety
14.3.1.1.2	Overall Summary of Treatment-Emergent and Post Treatment Adverse Events	Safety
14.3.1.2.1	Treatment-Emergent Adverse Events by MedDRA Preferred Term in the Order of Decreasing Frequencies (Safety Population)	Safety
14.3.1.2.2	Treatment-Emergent and Post Treatment Adverse Events by MedDRA Preferred Term in the Order of Decreasing Frequencies (Safety Population)	Safety

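### Renal response is summarised on mITT/pP, so a dosed subject who leaves before giving a post-baseline PCR is dropped instead of counted as a non-responder, which could slightly inflate the response rate

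*SAP*

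**What the plan says.** SAP 10.7.2 (renal response) and 10.7.3 (partial renal response) end with the same rule: "Subjects who discontinued prior to Week 12 will be counted as non-responders".

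SAP 8 fixes who is analysed: "The mITT and pP populations will be used for the summaries of the efficacy endpoints". The mITT population "includes all subjects who have received at least one dose of study drug, and have at least one post baseline urinary PCR assessment", and pP is a subset of mITT. The Safety Population has no PCR condition; it is "all subjects who have received at least one dose of study drug". Appendix A lists "Subjects Achieving Renal Response" twice, as Table 14.2.2.1 on MITT and Table 14.2.2.2 on PP. It has no version on the Safety Population and names no separate table for partial response.

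SAP 9.3 adds a general rule: "Subjects with missing values will not contribute to the denominator of percentage calculations". The SAP does not say how this fits with the non-responder rule.

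The PCR condition comes from the protocol. Under Protocol 7.6, ITT subjects are enrolled, "have received at least one dose of study drug, and have at least one post baseline urinary PCR assessment", and Protocol 7.10.4 places the main efficacy analysis in that population. The non-responder sentence appears only in the SAP.

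**The concern.** A non-responder rule exists so that dropping out cannot improve the response rate. It can act only on subjects who are in the table. A subject who takes CCX168, leaves within days and gives no later urine has discontinued before Week 12, so 10.7.2 and 10.7.3 would call that subject a non-responder. Section 8 has already removed the subject.

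Response is defined by the Day 85 PCR, so a subject with no post-baseline PCR can never be in the numerator. Removal can only leave the rate unchanged or raise it. The trial has one arm, so no comparator would suffer the same loss. Protocol 4.1 does not replace subjects who drop out after dosing, so each such loss comes out of a denominator of at most about 20.

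**Working it through.** **Who can be lost.** The relevant provisions, side by side:

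- First scheduled post-baseline PCR: Day 8 (Protocol Time and Events Table and 6.5).
- Withdrawal before Day 85: the Day 85 procedures are done as an Early Termination visit (Protocol 4.4 and 7.4). These include urine protein and creatinine (Protocol 6.10), but 4.4 asks for them only where they can be obtained.
- Exit for a fall in eGFR or a rise in proteinuria: needs confirmation by a repeat two weeks later, and the subject stays in the study (Protocol 3 and 4.4). Such a subject would normally have a Day 8 or Day 15 PCR and so be in mITT.
- Rescue treatment: the subject is asked to complete the remaining visits (Protocol 4.4).

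The subjects at risk are therefore mainly those who leave in about the first week, for example after an adverse event or on withdrawing consent, and give no termination sample.

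**Size.** The plan gives no expected response rate, dropout rate or number of subjects without a post-baseline PCR, so there is no figure of its own to reproduce. Its one design calculation concerns the PCR slope and does not bear on this point.

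Let N be the number dosed (up to about 20, Protocol 4.1), x the responders and k the dosed subjects with no post-baseline PCR. Both x and k are assumptions.

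- Rate on all dosed: x/N
- Rate on mITT: x/(N − k)
- Inflation factor: N/(N − k)
- Rise: x/(N − k) − x/N = xk/[N(N − k)]

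For N = 20 the factor is 20/19 = 1.053 (k = 1), 20/18 = 1.111 (k = 2) and 20/17 = 1.176 (k = 3). For N = 15 it is 1.071, 1.154 and 1.250.

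| N | x | All dosed | mITT, k = 1 | mITT, k = 2 | mITT, k = 3 |
|---|---|---|---|---|---|
| 20 | 2 | 10.0% | 10.5% | 11.1% | 11.8% |
| 20 | 4 | 20.0% | 21.1% | 22.2% | 23.5% |
| 20 | 5 | 25.0% | 26.3% | 27.8% | 29.4% |
| 20 | 10 | 50.0% | 52.6% | 55.6% | 58.8% |
| 15 | 5 | 33.3% | 35.7% | 38.5% | 41.7% |

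Example: x = 4, k = 1 gives a rise of 4 × 1/(20 × 19) = 1.1 percentage points; k = 2 gives 4 × 2/(20 × 18) = 2.2 points.

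For scale, the Clopper-Pearson 95% interval is 8.7% to 49.1% at 5/20 and 9.1% to 51.2% at 5/19. With k = 0 nothing changes. With x = 0 the estimate stays at 0%, and only the upper limit moves (16.8% at 0/20, 17.6% at 0/19).

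**The case against.** The strongest reply is that the sections do not contradict each other: Section 8 decides who is analysed, and 10.7.2 and 10.7.3 classify the people in that set. Applied in that order, both rules work, and the choice of denominator is a question of what is being estimated. The protocol made that choice first. This has force: the SAP did not depart from the protocol on the PCR condition. But the SAP's non-responder sentence has no exception, and read literally it covers subjects whom its own population excludes. A programmer has to decide which reading prevails, and the SAP does not say.

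The second reply is that the safeguards leave few people to lose. That is largely right. Stopping drug early is not enough; the subject must also miss Day 8, all later PCRs and the termination sample. A reader might infer that treatment failures are being removed from the denominator, or that the reported rate is certain to be inflated. The documents support neither. Subjects who exit for confirmed worsening stay in follow-up and would normally qualify for mITT, and inflation needs at least one excluded subject and at least one responder.

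The third reply is that nothing turns on it and any loss would show. Response is one of the other efficacy endpoints in SAP 7.2, reported as a count and percentage with a confidence interval and no test or threshold. Disposition is tabulated on both MITT and Safety (Tables 14.1.1.1 and 14.1.1.2), and Listing 16.2.2.3 shows efficacy against baseline on Safety. All of this stands. It limits the weight of the point, but a reader should not have to rebuild the response rate from a listing.

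**Conclusion.** The point holds as a minor one. For a dosed subject with no post-baseline PCR, the population in SAP 8 and Appendix A defeats the non-responder rule in 10.7.2 and 10.7.3, and the response rate could be slightly too high as a result. With 20 dosed, 4 responders and one or two such subjects, the rise is about 1 to 2 percentage points, small beside the sampling uncertainty. These counts are illustrative assumptions. The direction (zero or upward) is not an assumption; it follows from the definition of response. Neither the primary slope endpoint nor any formal decision is affected.

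**What to change.** - In SAP 8, 10.7.2, 10.7.3 and Appendix A, summarise renal and partial renal response on the Safety Population. Count subjects with no post-baseline or no Day 85 PCR because of discontinuation as non-responders.
- State that for these two endpoints this rule overrides the SAP 9.3 rule on missing values. Without that statement, 9.3 could remove the same subjects again after the change of population.
- Say in Appendix A where partial renal response is tabulated.
- Keep mITT for slopes and ratios, which need post-baseline data. Optionally report response on mITT as a sensitivity analysis.

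The cost is a few lines of SAP text and a table footnote, with no new data. The reported response rate may be slightly lower.

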9. DATA REVIEW AND PRESENTATION

9.1. Data Screening

In addition to the routine data review for individual subjects, all eCRF data will be periodically reviewed for consistency and accuracy across subjects. The periodic data review may involve ad hoc programming to generate edit checks. When available, tables, figures, and listings (TFL) may be used to identify data issues prior to the database lock.

9.2. Protocol Deviations

All protocol deviations will be classified as major or minor based on the following guidelines:

- Major protocol deviations are those that violate Good Clinical Practice (GCP) guidelines (ICH E6) and impact the ability to analyze the data collected. Examples may include but are not limited to: failure to administer the informed consent prior to initiating study procedures; non-compliance with taking study medication (less than 75% of medication taken based on study records or low plasma CCX168 concentrations indicating non-compliance); violations of inclusion and/or exclusion criteria that could affect the efficacy results.
- Minor deviations may include but are not limited to: out-of-window visits; scheduled assessments omitted or performed in improper sequence.

Protocol deviations will be categorized for data summary purpose.

9.3. Data Presentation

The following rules describe reporting conventions for the study.

- Report output will be provided as Rich Text Format (RTF) or Portable Document Format (PDF) documents generated using SAS.
- Font – Courier New or SAS font with minimum of 9 point font size for tables and 7 point for listings.
- Margins – Minimum of 3/4" bound edge margin and 3/8" other margins on 8.5"x11" paper as per the FDA guidance for e-submission.
- Continuous data will be summarized using n (number of subjects with non-missing observations), mean, median, standard deviation (STD), minimum value, and maximum value. Geometric means and geometric mean ratios (Visit:Baseline) will also be provided for urinary PCR, ACR, RBC count, MCP-1:creatinine, EGF:MCP-1 ratio, EGF:MCP-1 ratio, and serum IgA:plasma C3 ratio. Confidence intervals will also be provided for efficacy parameters.

- Categorical data will be summarized using the frequency count and percentage (n, %) of subjects in each category. Confidence interval for the percentage will be calculated for the efficacy variables.
- Number of subjects with non-missing values or number of subjects with missing values (eg, Not Done) will be presented, where appropriate. Subjects with missing values will not contribute to the denominator of percentage calculations.
- Counts of zero in any category will be presented without percentage.
- Precision of summary statistics:
 - Sample size (n, N) and number of missing responses (if displayed) – Integer.
 - Mean, confidence interval – One additional decimal place than reported/collected.
 - Standard deviation – Two additional decimal places than reported/collected.
 - Median, other percentile, minimum, maximum – Same number of decimal places as reported/collected.
 - Ratios – two decimal places.
 - Percentages – one decimal place generally, or two decimal places for <0.1%.
- Data listings will include pertinent subject information, eg, treatment, age/gender/race, study day. These will be sorted in the order of subject ID, assessment date/time and assessment (in the order collected on CRF, unless specified otherwise).
- Dates will be presented in the ISO-8601 format YYYY-MM-DD. Times will be displayed in 24-hour clock format.
- Numbering for tables, figures and listings will follow ICH E3 Guidelines.

10. STATISTICAL METHODS

10.1. Sample Size Justification

The sample size for the study is based on the slope of the urinary ACR observed in a study in patients with ANCA-associated vasculitis while receiving CCX168. The mean slope was -1.32, with a standard deviation of 1.67 over 12 weeks, and -4.62, with a standard deviation of 4.77 over the initial 4 weeks of the treatment with CCX168 in ANCA-associated vasculitis. Assuming a mean difference in pre-treatment and on-treatment slopes of 4.6, a sample size of 15 subjects will provide approximately 80% power and 20 subjects approximately 90% power to detect a difference in slopes.

10.2. General Statistical Methods and Data Handling

10.2.1. General Methods

Unless specified otherwise, all summary tables will be presented by visit from baseline to end of study (Day 169).

Summary statistics will be presented, as well as 2-sided 95% confidence intervals on selected parameters, as described in the sections below. All data will be included in the subject data listing.

10.2.2. Computing Environment

All statistical summaries and analyses will be performed using SAS software v9.4 or later, unless otherwise noted. Adverse events will be coded using MedDRA version 17.1. Concomitant medications will be coded using World Health Organization Drug Dictionary (WHODD) version March2012.

10.2.3. Grouping of Subjects

This is a single arm study. All subjects will be presented and summarized in the same treatment group.

10.2.4. Definition of Baseline

For all analyses, baseline will be defined as the most recent measurement prior to the date and time of the first administration of CCX168. Baseline can be on the same day as the first dose of study medication, but prior to administration of study drug (typically the Day 1 pre-dose value). For urinary PCR, baseline will be the geometric mean (GM) of the two measurements made in the Day -7 to -2 window plus the Day 1 (pre-dose) value. For the eGFR, urinary ACR, MCP-1:creatinine ratio, EGF:MCP-1 ratio, and microscopic RBC count, baseline will be the geometric mean of the one measurement made in the Day -7 to -2 window plus the Day 1 (pre-dose) value.

10.2.5. Methods of Pooling Data

No pooling of data with other studies is planned.

10.2.6. Adjustments for Covariates

Not applicable.

10.2.7. Multiple Comparisons/Multiplicity

Not applicable.

10.2.8. Subpopulations

Note applicable.

10.2.9. Withdrawals, Dropouts, Loss to Follow-up

Subjects who withdrew from the study will be included in the data listing and summary tables where applicable.

10.2.10. Missing, Unused, and Spurious Data

No imputation will be carried out for missing data points.

10.2.11. Visit Windows

No visit window will be used. All data will be summarized by the evaluation visit recorded on the eCRF. In data listings, all dates will be presented along with the study day relative to the day of the first dose of the study drug.

10.3. Interim Analyses

This is an unblinded single arm study. No formal interim analysis will be performed.

10.4. Subject Disposition

The number of subjects who have signed the informed consent, who entered the titration period, who entered the run-in period, who received study drug, who completed the 12-week treatment period of the study, who discontinued the 12-week period early (with reasons for discontinuation), who completed the

12-week follow-up period, who discontinued the 12-week follow-up period early (with reasons for discontinuation), will be tabulated.

A by-subject data listing of study completion information, including the reason for premature study withdrawal, if applicable, will be presented. If discontinuation is due to an AE, the AE will be specified.

Major and minor protocol deviations will be included in the subject data listing. Subjects with major protocol deviations affecting efficacy evaluation will be excluded from the pP population.

